8.8 MISSED SUBJECT VISITS

The Investigator shall inform study subjects of the importance of returning for scheduled follow-up visits and reporting any address or telephone number changes. The Investigator shall make every attempt to follow the study subjects.

The Investigator shall keep a separate log of the subjects' names and current contact information to facilitate their record keeping and ability to contact the subjects for future follow-up. If a subject cannot be reached for a follow-up assessment, the Investigator will document the missed visit and effort made to contact that subject, the subject's primary health care provider, and/or hospital records on the appropriate Case Report Form. Subjects who miss a visit will not be considered withdrawn, and an effort to contact them at the next follow-up visit interval will be made by the Investigator.

8.9 WITHDRAWAL CRITERIA AND PROCEDURES

The Investigator will make every attempt to follow the subjects at each of the required assessment periods. The reason for the withdrawal will be documented on the appropriate case report forms and in the medical records for each subject who has withdrawn.

Subjects may be withdrawn from the study for any of the following reasons:

- Subject Withdrawal

The subject may voluntarily withdraw from the clinical study at any time, without penalty or loss of benefits to which they are otherwise entitled.

- Physician Withdrawal

The Principal Investigator also has the right to withdraw a subject if they feel it is in the best interest of the subject to do so.

- Lost to Follow-up

If a subject cannot be reached for a follow-up visit, the Investigator will document the contact efforts made to the subject and/or effort to obtain hospital records in the appropriate electronic case report form. If the subject cannot be reached in any way, or misses a visit, the subject will be considered "unable to contact" for that time interval. After three (3) documented unsuccessful attempts to make contact prove unsuccessful, a certified letter will be sent to the subject's residence. If there is no response after the certified letter is sent, the subject will be considered "lost to follow-up."

In all cases of withdrawal (as described above), withdrawn subjects will not undergo further study follow-up procedures after the time of study exit. A study subject that has been withdrawn from the study will not be replaced.

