13 STATISTICAL ANALYSIS

13.1 SAMPLE SIZE

The primary endpoint is all-cause mortality at 30-days. Survival probabilities and standard errors will be estimated using the Kaplan Meier method and Greenwood formula respectively.

A performance goal of 18% was pre-specified for the 30-day rate of all-cause mortality in TVR (Tricuspid Valve Regurgitation) subjects treated with the Edwards FORMA Tricuspid Transcatheter Repair System, which was based on review of literature and early clinical studies (reference Section 1.3). The hypothesis for the primary endpoint is as follows:

- $H_0: \pi \geq 18\%$
- $H_A: \pi < 18\%$

Where π represents the all-cause mortality rate at 30 days.

The study is powered to detect a clinically significant difference between the expected mortality of the treatment group and the 18% Performance Goal. Based on the initial experience of the device (with some additional uncertainty assumptions), the estimated true rate was established to be 7.5% or less. Targeting a clinically significant difference of 10.5% (absolute reduction of greater than 50%), a sample size of 63 subjects will yield

at least 80% power to detect this difference at a significant level of 0.05. With a proportion of up to 9 investigational centers utilizing a roll-in subject and with a potential dropout rate of approximately 10%, an enrollment target of 78 subjects will ensure a sample size of 63 is available for analysis.

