3.2 Primary Endpoint Analysis

A performance goal of 18% was pre-specified for the 30-day rate of all-cause mortality in TVR (Tricuspid Valve Regurgitation) subjects treated with the Edwards FORMA Tricuspid Transcatheter Repair System, which was based on review of literature and early clinical studies. The hypothesis for the primary endpoint is as follows:

H0: $\pi \geq 18\%$

HA: $\pi < 18\%$

Where π represents the all-cause mortality rate at 30 days.

The primary endpoint for this clinical study is all-cause mortality at 30 days post-implant procedure in the as treated (AT) cohort population. A one-sided 95% confidence interval for 30 day mortality will be computed using the Kaplan-Meier algorithm with the standard errors being computed using Greenwood's formula. The null hypothesis shall be rejected at alpha = 0.05 if the upper confidence limit is less than 0.18.

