3.5 Missing Data Handling

All statistical analysis on the endpoints will be performed using only those patients with available data required for endpoint analysis. No missing value imputation will be performed.

No imputation will be done if the date variables are completely missing. For partial dates, only adverse event (AE) onset date will be imputed as follows:

- 1) If both month and day are missing
 - a. If the AE onset year is the same year as index procedure then use index procedure date to impute this AE onset date
 - b. Otherwise, assign January 1st for this AE onset date
- 2) If only day is missing
 - a. If the AE onset year and month are the same as the procedure ones then use the index procedure date to impute the AE onset date
 - b. Otherwise, assign '01' as the day for the AE onset date

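### A treated subject withdrawn before day 30 may have no recorded day-30 vital status, so the 30-day mortality test can be biased toward success if sicker subjects are the ones withdrawn

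*Protocol*

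**What the plan says.** **Withdrawal.** Protocol 8.9 lets the subject leave whenever they choose, and adds: "The Principal Investigator also has the right to withdraw a subject", on a judgement of the subject's best interest. It sets no time limit, so days 1 to 29 are included. In every case of withdrawal, "withdrawn subjects will not undergo further study follow-up procedures after the time of study exit".

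**What those procedures include.** Protocol 8.7 and Table 10 list the safety evaluation among the follow-up visit procedures. Protocol 8.10 keeps non-implanted and explanted subjects in safety follow-up to 6 months. Its entry for withdrawn subjects has no such provision. Checks with the care provider or hospital records are described for missed visits (8.8) and loss to follow-up (8.9), not for withdrawal.

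**A passage pointing the other way.** Protocol 12.1 has adverse events pursued until they resolve or are explained. Neither section says which applies to a withdrawn subject.

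**Analysis.** SAP 3.2 and Protocol 13.4 set the primary test in the As Treated cohort: "A one-sided 95% confidence interval for 30 day mortality will be computed using the Kaplan-Meier algorithm", with Greenwood standard errors and success if the upper limit is below 0.18. SAP 3.5 uses only patients with available data and adds: "No missing value imputation will be performed". Neither document states how a withdrawn subject enters the primary analysis, and neither plans a sensitivity analysis for unknown day-30 status.

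**The concern.** Kaplan-Meier treats a censored subject as having the same later risk as those still under observation. That is reasonable when the reason for leaving has nothing to do with prognosis. Here one route out is a decision by an investigator who knows the subject's condition, in a high-surgical-risk population, during the 30 days that define the endpoint. If the subjects who leave are those doing badly, a death after exit but before day 30 goes uncounted and the mortality estimate falls.

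The endpoint is a single pass/fail comparison with a fixed goal, and the number of deaths is small. One uncounted death can decide the result. Vital status at 30 days is also among the easiest outcomes to obtain without a study visit.

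**Working it through.** **Inputs from the documents**
- Goal: "A performance goal of 18% was pre-specified for the 30-day rate of all-cause mortality" (Protocol 13.1).
- Expected rate: "the estimated true rate was established to be 7.5% or less" (Protocol 13.1).
- Evaluable number: "a sample size of 63 subjects will yield" at least 80% power (Protocol 13.1).
- One-sided 95% upper limit, Kaplan-Meier with Greenwood, pass if below 0.18 (Protocol 13.4, SAP 3.2). I take z = 1.645.

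**Assumptions.** The documents do not say what share q of deaths is preceded by withdrawal. They also do not say whether the limit is untransformed or on the log-log scale, so both are shown.

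**Step 1: the plan's own figure.** With an exact one-sided binomial test at n = 63 and success at 6 or fewer deaths:
- P(X ≤ 6 | 0.18) = 0.0487
- P(X ≤ 6 | 0.075) = 0.808

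This reproduces 63 subjects for at least 80% power.

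**Step 2: untransformed limit, every death counted.** With no censoring, Greenwood reduces to SE = √[p(1−p)/n], and the limit is p + 1.645 × SE.
- 7 deaths: p = 7/63 = 0.1111, SE = 0.0396, limit 0.176 (pass).
- 8 deaths: p = 8/63 = 0.1270, SE = 0.0419, limit 0.196 (fail).

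**Step 3: 8 true deaths, one hidden by withdrawal** (7 counted, 1 censored).
- Censored before the first death: p = 7/62 = 0.1129, SE = 0.0402, limit 0.179 (pass).
- Censored after the last death: as 7/63, limit 0.176 (pass).

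Every position in between lies between these values. Dropping the subject altogether, which the available-data wording of SAP 3.5 could also mean, gives 7/62 and 0.179 as well.

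**Step 4: log-log limit.** Let S be survival and G the sum of 1/[r(r−1)] over deaths, with r the number at risk. The upper mortality limit is 1 − S^exp(1.645 × √G / |ln S|).

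| True deaths | Counted | Censored | Upper limit | Result |
|---|---|---|---|---|
| 6 | 6 | 0 | 0.178 | pass |
| 7 | 7 | 0 | 0.197 | fail |
| 7 | 6 | 1, before first death | 0.1807 | fail |
| 7 | 6 | 1, between first and second | 0.1803 | fail |
| 7 | 6 | 1, after second or later | 0.178 to 0.180 (below 0.18) | pass |

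On this scale the reversal depends on when the subject leaves.

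**Step 5: chance of false success at 18% true mortality.** Draw D deaths from Binomial(63, 0.18), hide each with probability q, compute the limit, and add up the probability of a pass. The range runs from all hidden subjects censored before the first counted death to all censored after the last.

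| q (assumed) | Untransformed | Log-log |
|---|---|---|
| 0 | 9.9% | 4.9% |
| 5% | about 13% | about 5% to 7% |
| 10% | about 15% to 18% | about 6% to 10% |

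The 9.9% at q = 0 arises because the untransformed limit passes at 7 deaths where the exact test passes at 6. It has nothing to do with withdrawal. The effect of withdrawal is the difference from the first row: at q = 10%, about 5 to 8 points untransformed and 1 to 5 points log-log.

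**Step 6: at the planned rate.** At 7.5% mortality about 63 × 0.075 = 4.7 deaths are expected. With q = 10% the untransformed chance of success moves only from about 90% to about 94%.

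**The case against.** The case against has real force.

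- **A reader might infer that the test is biased as a matter of fact.** The documents do not support that. Protocol 8.9 speaks of the subject's best interest and mentions neither deterioration nor palliative care. Withdrawal unrelated to prognosis adds no bias, and nothing shows that early withdrawal would be common or linked to outcome. This stands, so the point is conditional.
- **A reader might infer that all follow-up ceases.** The text covers study follow-up procedures. Protocol 12.1 has adverse events followed to resolution and serious events reported within 24 hours, and 12.3.1 asks for every effort to obtain death documents. A deteriorating subject may already have an open serious event. This also stands in part. But 12.1 describes treatment while study follow-up goes on, and it does not require day-30 status for each withdrawn subject. The listings of deaths for all enrolled subjects can show only deaths that are known.
- **A reader might take the dropout allowance as support for q = 10%.** Protocol 13.1 allows for dropout "with a potential dropout rate of approximately 10" per cent, but that is a share of subjects, not of deaths. It may include subjects who exit before any incision and never enter the As Treated cohort. The allowance does not support the assumed share.
- **Text that cannot be seen.** Investigator reports, sponsor reports, monitoring committee details and stopping rules are blacked out, and the consent form is not available. A vital-status provision could sit there, so the statement is limited to the visible text.
- **Counting every unknown as a death is severe.** Five deaths and three unknowns in 63 would then be 8 events, a limit of 0.196 and a fail. A tipping-point analysis is the better main tool.

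**Conclusion.** The point holds in conditional form. The visible plan permits withdrawal of a treated subject before day 30, ends study follow-up procedures at that moment, and does not require day-30 vital status. Censoring at exit is inferred from the Kaplan-Meier method, since no rule is written; exclusion would act in the same direction. If sicker subjects are the ones withdrawn, the primary test can be biased toward success.

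At 63 subjects a single hidden death reverses the untransformed result when there are 8 true deaths. It can reverse the log-log result when there are 7, depending on when the subject leaves. The false-success figures rest on the assumed share of deaths following withdrawal. At the planned 7.5% mortality the effect is small. This is a gap worth closing because it touches the pass/fail test and is cheap to close; it is not a demonstrated bias.

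**What to change.** - **Protocol 8.9:** state that withdrawal from study visits, by either route, does not end collection of day-30 vital status for As Treated subjects. Obtain it by telephone, care provider, hospital record or public registry unless the subject refuses.
- **Protocol 8.9 and 12.1:** reconcile the end of follow-up procedures with the continued pursuit of adverse events for withdrawn subjects.
- **SAP 3.2:** state how a subject withdrawn before day 30 enters the Kaplan-Meier estimate. Add a supportive tipping-point analysis for As Treated subjects with unknown day-30 status, showing how many would have to have died to change the conclusion, with all unknowns counted as deaths as its extreme.

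The cost is a few status checks, one sentence in the consent form and one extra analysis. The reported mortality may be slightly less favourable.

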8.10 SUBJECT STUDY COMPLETION

Study subjects complete and exit the study when no additional follow-up visits, procedures, or data collection are required. Patients will then continue to be followed by their primary health care provider as required.

A subject will also be exited from the study in the following instances:

- Subject signs informed consent form, is deemed eligible and considered enrolled but does not undergo the study procedure
- Subject undergoes study procedure and does not receive investigational device (will continue in study for safety evaluations only and exit the study at the 6 month follow-up visit)
- Implanted subject requires the investigational device to be explanted for any reason (will continue in study for safety evaluations only and exit the study at the 6 month follow-up visit)
- Subject is lost-to-follow-up
- Subject withdraws participation from the study or is withdrawn from the study
- Subject expiration

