7.2 INCLUSION CRITERIA

The Investigator has the responsibility of screening potential subjects to determine if the patients meet all the inclusion criteria. The following are requirements for entry into the study:

1. Signed and dated EC approved study consent form prior to study related procedures
2. Eighteen years of age or older
3. Clinically significant, symptomatic (NYHA Functional Class II or greater), tricuspid regurgitation (Stage D per 2014 AHA/ACC guidelines) requiring tricuspid valve repair or replacement as assessed by the Heart Team
4. Functional tricuspid regurgitation (e.g., EROA \geq 0.4 cm² or equivalent guideline directed value) as the primary etiology
5. NYHA Functional Class II or greater or signs of persistent right heart failure despite optimal medical therapy
6. Determined by the 'HEART Team' (a minimum of one Cardiologist, and one Cardiac Surgeon) to be at high surgical risk for tricuspid valve repair or replacement and the benefit-risk analysis supports utilization of the investigational device
7. Willing to attend study follow-up assessments for up to 3 years

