8.6 IMPLANT PROCEDURE

The implant procedure shall be performed under general anesthesia with hemodynamic monitoring in an operating room, catheterization lab or hybrid operating room with fluoroscopic and echocardiographic imaging capabilities. The use of cardiopulmonary bypass is not required.

The following study procedures will occur during the implant procedure:

1. Safety Evaluation
2. Transesophageal Echocardiogram
3. Angiographic Imaging
4. Invasive Hemodynamic Monitoring/Right Heart Catheterization including right atrial pressure measurements pre and post implant
5. Heparin administration to achieve (and maintain) an ACT of ≥ 250 during the implant procedure

Subjects will be monitored in the operating room as needed with special attention to hemodynamic condition and cardiac rhythm. Subsequent monitoring of subjects will be continued in the recovery room or ICU.

The date of the implant procedure will be considered as Day 0 for the purpose of determining specified time intervals for the follow-up visit for the implanted and non-implanted cohorts.

Procedure data to be collected will include but is not limited to the information listed in the following table.

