**Table 9 - Follow-up Visit Windows**

Scheduled Follow-up Interval	Follow-up Window
1 month (30 days)	± 7 days
6 months (183 days)	± 30 days
Annually (365 days) up to 3 years	± 45 days

During the follow-up visits, medical information, findings and results will be entered in the appropriate electronic case report forms.

Study subjects who have signed the Informed Consent, are deemed eligible and considered enrolled in the study but do not have the study procedure (incision) occur will be exited from the study immediately.

Study subjects who have signed the Informed Consent, are enrolled in the study, have the study procedure (incision) occur but do not receive the investigational device will be classified as “non-implanted” study subjects and exit the study at the 6 month follow-up visit. Non-implanted study subjects must complete safety evaluations but, will be exempt from all other study follow-up visit procedures.

Table 10 - Summary of Required Study Procedures

STUDY PROCEDURES	BASELINE	IMPLANT PROCEDURE ¹ (Day 0)	DISCHARGE ²	1 MONTH (30 ± 7 days)	6 MONTHS (183 ± 30 days)	ANNUAL (for 3 yrs) (365 ± 45 days)
Informed Consent	X					
Medical History	X					
Clinical Evaluation	X		X	X	X	X
NYHA Class Assessment	X			X	X	X
Health Status Questionnaires	X			X	X	X
Six Minute Walk Test	X			X	X	X
Safety Evaluation		X	X	X	X	X
Brain Natriuretic Peptide (BNP)	X		X	X	X	X
CBC and Platelet Count	X		X	X	X	X
Complete Metabolic Panel	X		X	X	X	X
Liver Panel	X		X	X	X	X
PTT/aPTT or PT/INR	X		X	X	X	X
βHCG	X ³					
eGFR	X ⁴		X	X	X	X
Troponins and CK-MB	X	X ⁵	X ⁶			
ECG	X		X	X	X	X
Transesophageal Echocardiogram	X ⁷	X				
Transthoracic Echocardiogram	X		X	X	X	X
Pre-Implant Computed Tomography	X					
Angiographic Imaging		X				
Invasive Hemodynamic Monitoring/Rt Heart Cath.	X ⁸	X				

¹ Implant procedure must be scheduled within 90 days of the baseline transthoracic echocardiogram and 90 days of the pre-implant procedure computed tomography (CT). If a pre-existing CT within 6 months of the scheduled implant captures all the required anatomy for necessary measurements & the anatomy has not changed, the baseline CT can be waived & is not required to be repeated.

² Discharge from hospital/unit post implant procedure

³ βHCG for women who are not sterile or post-menopausal

⁴ eGFR result of < 25 is an exclusion from study participation

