13.5 ADDITIONAL ENDPOINT ANALYSIS

All statistical analyses will be performed by Edwards Lifesciences. Subject data listings and tabular presentations of results will be provided. All clinically relevant baseline and follow-up variables will be tabulated. Descriptive statistics will be used for continuous variables (e.g., mean, standard deviation, sample size, minimum, and maximum) and frequency tables or proportions for discrete variables.

Kaplan Meier estimates will be performed at the pre-specified follow-up times to project the estimates for time-related safety endpoints. The rate of freedom from all-cause mortality at 6 month, 1 year, 2 years, and 3 years will be estimated in addition to the primary endpoint which is established at 30 days post procedure.

Echocardiographic data will be analyzed by a core laboratory. The improvement from baseline items will be presented as shift from baseline for each of the pre-specified follow-up periods. Subjects that are missing a baseline or follow-up values will be excluded from the analysis.

Subjects that undergo any type of repair or replacement procedure for the tricuspid valve will be excluded from the implant cohort analyses at the time of the re-intervention.

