Device Detachment	Separation, under the action of applied stress or strain, of any part of the investigational device that was previously intact.
Device Embolization	Refer to ISO 5840-3 definition
Device Malfunction	Refer to ISO 14155 definition
Device Migration	Refer to ISO 5840-3 definition
Device Success	
Device Success (at 1 month, 6-months and annually):
 
 • Alive, with • Original intended device in place, and • No additional surgical or interventional procedures related to the device, and • TR reduction (assessment made by change in EROA) compared to baseline and TV gradient $\leq 5\text{mmHg}$
Embolism	
Free flowing blood clot or lesion material that is located in the systemic or pulmonary circulation.
 
A peripheral embolic event is an operative, autopsy or clinically documented embolus that produces symptoms from complete or partial obstruction or a peripheral (noncerebral) artery.

Emergency Surgery
	
Emergent Salvage: The patient is undergoing CPR en route to the operating room or prior to anesthesia induction
 
Emergent: All of the following conditions are met:
 
 • Not elective status • Not emergent salvage status • Procedure required before procedure room exit in order to minimize chance of further clinical deterioration • Any surgical procedure on the previously implanted study device (repair, alteration or replacement) or study procedure access site post-implant procedure 
Elective: The patient’s cardiac function has been stable in the days or weeks prior to the operation. The procedure can be deferred without increased risk of compromised cardiac outcome.

Endocarditis
	
An inflammation of the inside lining of the heart chambers and heart valves (endocardium). Endocarditis can involve the heart muscle, heart valves, or lining of the heart.

Enrollment
	
Subject enrollment in this clinical study is established when a subject has signed the informed consent form agreeing to participate in the study and has been deemed eligible for study participation by meeting the study criteria.

Explant
	
Removal of the study device after completion of the implant procedure for any reason.

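### Non-implanted and explanted subjects leave at the 6-month visit, so the planned 1- to 3-year survival estimates are probably informatively censored, and the exit rule does not cover an explant after month 6

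*Protocol*

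**What the plan says.** Protocol 8.10 names two groups that stay for safety evaluation only and then leave early. The first is subjects who undergo the procedure but receive no device. The second is: "Implanted subject requires the investigational device to be explanted for any reason (will continue in study for safety evaluations only". Both are to "exit the study at the 6 month follow-up visit". Protocol 8.7.1 repeats the rule for the first group: "Non-implanted study subjects must complete safety evaluations but, will be exempt from all other study follow-up visit procedures".

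Protocol 13.5 says: "The rate of freedom from all-cause mortality at 6 month, 1 year, 2 years, and 3 years will be estimated". SAP 3.3 says the same. Both specify Kaplan-Meier and neither names the cohort. Protocol 13.6 and SAP 3.5 rely on available data without imputing outcomes. No contact after exit is described, and no sensitivity analysis for censoring is planned. Protocol 13.5 and SAP 3.3 also remove subjects from the implanted-cohort analyses once they have any tricuspid repair or replacement.

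Other sections promise longer follow-up. Protocol section 6 states 3 years for all enrolled subjects. Protocol 8.7.1 and SAP 2.3 state 3 years for all implanted subjects.

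**The concern.** Kaplan-Meier is unbiased only if those censored go on to die at the same rate as those who remain. Here censoring is not administrative. It happens because the device could not be placed or had to be removed. If those subjects fare worse after month 6, their deaths are unseen and the curve describes mainly subjects who kept the device. The study is a safety study with outcomes to 3 years and is meant to support regulatory approval (Protocol section 2), so an optimistic long-term survival figure would matter.

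There is also a gap in the rule. Visits are counted from the implant, and an explant can occur at any time. For a late explant, the visit at which the subject should leave has already passed.

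**Working it through.** **The plan's own figure.** The documents give no number for the exit rule or for survival beyond 30 days. The nearest stated figure is the sample size of 63 (Protocol 13.1). With a goal of 18%, a true rate of 7.5% and one-sided alpha of 0.05, an exact binomial test at n = 63 rejects with 6 or fewer deaths. Its alpha is 0.0487 and its power 0.808, so the figure reproduces. The endpoint is at day 30 and the earliest exit visit is day 183 − 30 = 153, so the exit rule cannot affect it.

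**How much follow-up is lost.** From day 183 to day 1095 is (1095 − 183)/1095 = 83% of the 3-year period. Across the visit window (days 153 to 213) it is 86% to 81%.

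**First illustration (all inputs assumed).** Survival at 6 months is 90% in all subjects. Retained subjects then die at 15% per year, so h = −ln(0.85). A fraction f of those alive exits at 6 months, with hazard ratio HR against the retained.

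- Kaplan-Meier at 3 years = 0.9 × exp(−2.5h) = 0.9 × 0.666 = 60.0%
- True value = 0.9 × [(1 − f) × exp(−2.5h) + f × exp(−2.5h × HR)]

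True 3-year survival in %, with the error of Kaplan-Meier in percentage points:

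| f | HR 0.5 | HR 1 | HR 2 | HR 3 |
|---|---|---|---|---|
| 5% | 60.6 (−0.7) | 60.0 (0) | 58.9 (+1.0) | 58.3 (+1.7) |
| 10% | 61.3 (−1.4) | 60.0 (0) | 57.9 (+2.0) | 56.6 (+3.3) |
| 20% | 62.7 (−2.7) | 60.0 (0) | 55.9 (+4.0) | 53.3 (+6.7) |

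At 1 year the overstatement for HR 2 to 3 is 0.3 to 2.5 points. Bounds at 3 years (all exited die, or none die) are 54.0% to 63.0% for f = 10% and 48.0% to 66.0% for f = 20%.

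**Second illustration (also assumed).** The two groups differ from day 0. Retained subjects die at 15% per year and exiting subjects at 30% or 45%. The hazard ratios are ln(0.70)/ln(0.85) = 2.2 and ln(0.55)/ln(0.85) = 3.7. True survival is (1 − f) × 0.85³ + f × 0.70³ (or 0.55³). Kaplan-Meier gives S(0.5) × 0.85^2.5.

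- f = 5%: overstated by 1.1 to 1.6 points
- f = 10%, 30% per year: 58.7% true against 60.8% (+2.1)
- f = 20%, 45% per year: 52.5% true against 59.0% (+6.6 before rounding)

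The upper ends are not ceilings. Putting HR 3.7 into the first model at f = 20% gives 0.9 × 0.20 × (0.666 − 0.224) = 8.0 points.

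**Which subjects count.** The Implanted cohort (Protocol 13.3) contains only subjects who leave the procedure room with the device. Non-implanted subjects therefore affect survival only in the As Treated or Enrolled cohort. Explants affect it in the Implanted cohort too.

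**Late explant.** Protocol 8.6: "The date of the implant procedure will be considered as Day 0". The 6-month visit is day 183 ± 30 (Table 9). Protocol section 19 defines an explant without a time limit: "Removal of the study device after completion of the implant procedure for any reason". Protocol 12.3.2 provides for explants in the late post-operative period. An explant at month 14, for example, has no exit visit ahead of it, and a death that follows it may not be recorded.

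**The case against.** - **The bias is inferred.** The documents give no explant or non-implant rate and no mortality for these subjects. Equal hazards give no bias and a lower hazard reverses it. This stands. A reader might infer that survival is biased in the device's favour as a matter of fact; the documents do not establish that. They only make the direction plausible. Protocol 1.1.2 ties more severe regurgitation to worse survival, and Table 1 lists in-hospital mortality of 35.1% and 37% at re-operation. The latter is surgical literature and only indicative.
- **The weight is modest.** Long-term survival is descriptive and carries no hypothesis test. With 63 subjects and 60% survival (assumed), a 95% interval is about ±1.96 × √(0.6 × 0.4/63) = ±12 points, wider than most of the shifts above. This stands, but the interval does not allow for the bias.
- **Failures are not erased from every output.** One might read the rule as removing device failures altogether. However, Device Success (Protocol 5.2.2) requires the original device to be in place, so an explanted subject cannot meet it. The point is confined to survival after exit.
- **Late explant.** The list in 8.10 is headed as instances of exit, so leaving at the explant is a natural reading once month 6 has passed. The wording is therefore a gap to close, not a wrong number.
- **Consent.** It is tempting to say subjects already agreed to 3 years. The criterion reads: "Willing to attend study follow-up assessments for up to 3 years". That is compatible with early exit, and the consent form is not available here.

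**Conclusion.** The point holds in a limited form. The exit rules make censoring of 1- to 3-year survival depend on procedure or device failure, so it is probably informative. Under the assumed rates (5–20% exited; hazard ratio 2 to 3 in one model, 2.2 to 3.7 in the other), 3-year survival is overstated by about 1 to 7 points. There is no bias at a ratio of 1, and the sign reverses below it.

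Size and direction rest wholly on those assumptions and on a cohort the plan does not name. What needs no assumption is that the cohort is unnamed, that an explant after month 6 has no workable exit point, and that the follow-up statements contradict each other. A reader might also infer that the main result is at risk. It is not, because the only hypothesis test is complete at day 30.

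**What to change.** In Protocol 8.7.1 and 8.10, collect vital status only, to 3 years, by telephone or record check in the annual windows. Apply this to all treated subjects, including non-implanted and explanted ones, provided consent covers the contact. State that the same applies to an explant after month 6. Reconcile these sections with Protocol section 6 and SAP 2.3.

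In SAP 3.3, name the As Treated cohort for 1- to 3-year survival and include these subjects. Report a worst-case bound counting any not reached as dead. The exclusion at re-intervention is written for the implanted cohort, so it would not remove anyone from this estimate.

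The cost is a few contacts per year for a small group (5–20% of 63 is about 3 to 13 subjects) and possibly a clarification of the consent form. No visits or procedures are added, and sites already keep contact logs (Protocol 8.8). This is a cheap improvement.
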